## 1 PURPOSE OF EXTENDING THE STUDY

**The purpose of extending the study was to evaluate the efficacy of bleomycin-based electrochemotherapy in treating colorectal liver metastases in a phase II clinical study.**

The purpose will be achieved by:

- applying treatment in a controlled manner based on pre-clinical experience and the clinical experience of the ESOPE project;
- evaluating procedures and results achieved;
- preparing standardized procedures;
- disseminating these new approaches to treatment using written and audio-visual materials as well as by attending and organizing expert meetings.

**The study is designed as an institutional study (Institute of Oncology Ljubljana) conducted in cooperation with the Faculty of Electrical Engineering (University of Ljubljana), University Medical Centre Ljubljana and industrial partner, IGEA srl., Carpi, Italy, which will provide technical support for the study. An additional 15 patients who meet the inclusion criteria will be included in the extended part of the study.**

The study will be carried out within the P3-0003 "Razvoj in ovrednotenje novih terapij za zdravljenje malignih tumorjev" (Development and evaluation of new therapies for treating malignant tumours) research programme headed by [name], PhD.

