A phase I/II clinical study is currently underway at Institute of Oncology Ljubljana to assess the safety and efficacy of treatment for colorectal liver metastases using ECT. We wish to include an additional fifteen (15) patients within phase II using this protocol. To date, 17 patients have been included in the clinical study, and preliminary results in 16 of these patients indicate that treating colorectal liver metastases and one HCC patient using ECT is a safe method for treating tumours even in hard-to-reach locations. Preliminary MRI results in all patients testify to radiological changes similar to those observed after RFA treatment. The response to ECT treatment was complete in 50% of patients and partial in the remaining 50% of patients. Preliminary histological analysis results for all ECT-treated metastases after surgical removal indicate progressive degenerative changes within metastases and a statistically significant reduction in viable tumour tissue in ECT-treated metastases compared to non-ECT-treated metastases ( $p < 0.001$ ). We were the first to publish the technological part of the procedure in the clinical case.

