#### 3.1 Inclusion criteria

1. Patients with one to three (1–3) metachronous colorectal liver metastases, up to 5 cm in size, that are difficult to resect due to their position (likelihood of insufficient healthy liver after resection) or inaccessible for treatment with standard ablation techniques because they are located on large hepatic vascular structures (portal veins, hepatic veins or their inflow into the inferior vena cava, immediate vicinity of vena cava), but are otherwise operable.
2. Patients with up to three (3) recurring colorectal liver metastases, each with a maximum diameter not exceeding five (5) cm, and for which other treatment is either unacceptably risky due to possible insufficient residual liver volume after resection or expected to be less effective due to the proximity of veins in RFA.

*Patients in groups 1 and 2 are patients in whom standard treatment options (systemic and/or surgical) have been exhausted. ECT will be offered to these patients as the only therapeutic option. If a patient has a large number of metastases that are unresectable and at the same time unsuitable for RFA, the metastases will be treated with ECT, while any other metastases will be resected or treated with RFA.*

3. Patients with synchronous colorectal liver metastases, in whom—due to their poor general health or the extent of the disease—first the removal of the primary tumour is planned, and after 2–3 months, surgery on the metastases, with systemic treatment taking place in the meantime. ECT would be used to treat metastases up to 5 cm in maximum diameter during the first surgical procedure, i.e. when the primary tumour is removed.
4. Patients with bilateral metachronous colorectal liver metastases who require two-stage surgery due to the extent of the disease, i.e. right portal vein ligation and excision or RFA of metastases in the left hepatic lobe at the first stage and right hepatic lobe resection at the second stage. During the right portal vein ligation surgery, the metastases should be accessible in order to apply electroporation pulses without major manipulation and mobilization of the liver, so as not to create additional problems for the second planned procedure, i.e. the removal of metastases by resecting the right hepatic lobe.

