### 6.1. Effects of treating colorectal liver metastases using ECT

- Early treatment effects will be assessed using DCE-US or CT based on changes in tumour blood flow after ECT compared to pre-ECT blood flow.
- Late effects will be assessed based on modified RECIST criteria, taking into account the change in the size and density of treated tumour nodules before and after ECT. These will be assessed based on DCE-MRI images; the volume of the metastases will be calculated using the formula  $V = \frac{a \times b^2 \times \pi}{6}$ , where a is the shorter and b the longer metastasis diameter.

Based on the assessment of the late ECT effects, the response to treatment will be evaluated in line with the WHO classification:

- Complete response (CR): complete disappearance of the tumour nodule
  - Partial response (PR): reduction of tumour nodule size by more than 50%
  - No change (NC): decrease in tumour nodule size by less than 50% or increase in tumour nodule size by less than 25%
  - Progressive disease (PD): growth of the tumour nodule by more than 25%
- The direct effect will be assessed by histological analysis of those metastases that will be surgically removed.
  - EORTC Quality of Life questionnaire according to QLQ C30 standards

EXAMINATION/TEST	Screening period until D -14	D -1	D 7	D 30	D 60	D 90	D 120
clinical examination, anamnesis	X	X	X	X	X	X	X
ECG	X	X					

DCE-MRI	X			X		X
DCE-US	X			X	X	X
CT perfusion	X			X		X
Blood count	X	X	X			
Coagulation tests	X	X	X			
Biochemical blood analysis	X	X	X	X	X	X
EORTC QLQ C30 questionnaire	X		X	X		

\*D = day

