## **8 STATISTICAL ANALYSIS**

All data will be entered into a Microsoft Access 2010 database, which will be used for all calculations except for statistical analysis, which will be performed with GraphPad Software (La Jolla, CA, USA). The log-rank (Mantel-Cox) test will be performed on the Kaplan-Meier estimates. A chi-squared test will

be used for the statistical comparison of response according to tumor location. A two-tailed P value less than 0.05 will be considered to be statistically significant.

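### The chi-squared test of response by tumour location is a large-sample test on tables too sparse for it: its true error rate can lie below 1% or, in very uneven tables, near 12%, and an exact P value should replace it

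*Combined protocol and SAP*

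**What the plan says.** Section 8 names one comparison of response. A chi-squared test will "be used for the statistical comparison of response according to tumor location", and the threshold is set there too: "A two-tailed P value less than 0.05 will be considered to be statistically significant". It mentions no exact test, continuity correction, minimum expected count or fallback.

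On size, Section 1 says: "An additional 15 patients who meet the inclusion criteria will be included in the extended part of the study". Section 2 (Treatment of liver tumours) adds: "To date, 17 patients have been included in the clinical study". The plan does not say whether the two sets are pooled for this test.

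On the response scale, Section 6.1 says: "Based on the assessment of the late ECT effects, the response to treatment will be evaluated in line with the WHO classification". That gives four classes (CR, PR, NC, PD), each defined for a nodule, for example "Complete response (CR): complete disappearance of the tumour nodule". A patient may contribute several nodules. Inclusion group 1 in Section 3.1 reads: "Patients with one to three (1–3) metachronous colorectal liver metastases, up to 5 cm in size".

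The plan does not define the location groups, whether response is collapsed to yes/no, or whether patients or nodules are counted. Section 7 describes the analysis as descriptive.

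**The concern.** The chi-squared P value is a large-sample approximation, usually trusted when expected counts are about 5 or more per cell. A table from 15 patients cannot meet that. The preliminary liver results also suggest that non-response is rare: "The response to ECT treatment was complete in 50% of patients and partial in the remaining 50% of patients". If so, the NC and PD cells will be nearly empty.

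In such tables the nominal 5% need not be the rate at which a location effect is wrongly declared, and a single patient can carry the result. Location matters to this protocol, whose rationale includes lesions beside large vessels where radiofrequency ablation works poorly. A spurious location effect would be read in that light.

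**Working it through.** The plan gives no error rate, power or sample-size derivation to reproduce. The only stated figures are the nominal 0.05 and the 15 patients.

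**Inputs from the documents.** n=15 (Section 1); 17 earlier patients, so 17 + 15 = 32 if pooled (Section 2); four response classes (Section 6.1); up to three metastases in group 1, so up to 15 x 3 = 45 nodules (Section 3.1).

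**Assumptions.** Number and sizes of location groups, response rates, the patient as unit, independent patients, and the uncorrected Pearson statistic.

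**1. Expected counts.** They sum to n. For all to be at least 5, a 2 x 2 table needs 4 x 5 = 20 patients and a 2 x 4 table needs 8 x 5 = 40. The first exceeds 15; the second exceeds even the pooled 32.

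**2. One non-responder.** Suppose one of k patients at a location does not respond and all others in the study do. Then chi-squared = n(n-k)/((n-1)k). With two locations the exact (Fisher) P is k/n. For n=15:

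| k | Statistic | P, two locations | P, three locations | Exact P, two locations |
|---|---|---|---|---|
| 1 | 15 x 14/(14 x 1) = 15.0 | 0.0001 | 0.0006 | 0.067 |
| 2 | 15 x 13/(14 x 2) = 6.96 | 0.008 | 0.031 | 0.133 |
| 3 | 15 x 12/(14 x 3) = 4.29 | 0.038 | 0.117 | 0.200 |
| 4 | 15 x 11/(14 x 4) = 2.95 | 0.086 | 0.229 | 0.267 |

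One patient is therefore enough at k of 3 or less with two locations, and at k of 2 or less with three. With 32 patients and two locations, k=6 gives 0.034 against an exact 6/32 = 0.19.

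**3. True error rate, yes/no response, n=15.** All tables were enumerated with the same response rate at each location, and the probabilities of those with P<0.05 were summed.

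| Locations | Response rate | True rate at nominal 5% |
|---|---|---|
| 4/11, 5/10, 6/9, 7/8 | 50-90% | 0.7% to 5.1% |
| 2/13 | 50-90% | 2.3% to 5.5% |
| 3/12 | 80-90% | 6.0% to 8.7% |
| 1/14 | 80-90% | 8.4% to 9.7% |
| 1/14 | 50% | 0.65% |
| 1/1/13 | 80%, 90% | 9.5%, 12.05% |
| 1/2/12 | 90% | 12.0% |
| 5/5/5 | 90% | 0.96% |
| 1/1/13 | 50% | 0.7% |

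Over all three-location splits and six response rates from 50% to 90%, 12.3% of the combinations exceed 7.5% and 20.2% fall below 3%.

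**4. True error rate, four WHO classes, n=15.** By simulation, with assumed CR/PR/NC/PD of 45/45/5/5, 60/30/5/5, 70/20/5/5 and 40/40/15/5% and empty classes dropped: split 2/13, 7-10%; 1/2/12, 7-11%; 1/1/2/11, 8-12%; 5/10, 3-4%.

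**5. Other sample sizes.** With three locations and yes/no response, the range is 0.04% to 12.6% at n=32, and about 0% to 14.4% at 45 nodules treated as independent. A larger count does not remove the problem when some locations are nearly empty.

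**6. Price of an exact test.** With two locations and yes/no response at 50-95%, Fisher's true level is 0% to 3.5%. At split 5/10, with the lower rate at the smaller location, power is:

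- 30% vs 90% response: Pearson 78%, Fisher 54%.
- 40% vs 95% response: Pearson 79%, Fisher 52%.

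Boschloo's test at 5/10 rejects exactly the tables that Pearson rejects (largest true level 4.9998%), so it keeps the 78% and 79%.

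With four classes (10/60/20/10% vs 70/25/3/2%), chi-squared against exact power is 55% vs 59% at 5/10, 54% vs 57% at 7/8, and 52% vs 47% at 3/12.

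**The case against.** The strongest reply is that the large figures come from assumed tables.

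- **Two-way contrasts.** The contrasts the protocol itself suggests are two-way: depth up to or beyond 3 cm (Sections 4 and 5.2.2), and near large vessels or not (Sections 3.1 and 5). For two-way splits of 4/11 to 7/8 the test holds about 5%.
- **The preliminary data are benign.** Half CR and half PR, with nothing else, makes a 2 x 2 table at 50%. Pearson's true rate there is 4.2% to 5.1% for splits 3/12 to 7/8, against 1.7% to 3.5% for Fisher.
- **A Yates correction** would remove the 2 x 2 inflation: true rate at most 1.5%, and P=0.072 for one non-responder at k=1.
- **Fisher alone** can cost 24 to 27 points of power where Pearson already holds its level.
- **The unit may be the nodule.** A plain exact test would then ignore clustering just as chi-squared does.

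All of this stands as a limit on the size of the point and on the choice of remedy. It does not save the stated test. Section 8 does not restrict the table to 2 x 2, does not mention a correction, and offers no alternative when cells are sparse. Yates does not apply beyond 2 x 2, and leaving it unstated makes P at k=1 either 0.0001 or 0.072.

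A reader might infer that this test has a 12% error rate. The documents do not support that: 12% needs three or more locations, some with 1-2 patients, together with response near 90% or sparse response classes. The plan fixes none of these.

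**Conclusion.** The point holds in a limited form. Section 8 applies a large-sample test, with a significance threshold, to a sample that cannot meet the usual condition for it. The 5% is close to true for two reasonably filled locations when response is not near 100%. It is exceeded in very uneven two-way splits and more clearly in sparse larger tables, and it is far from reached in others. The single-patient result follows from algebra, but needs an uncorrected test, a location of at most 3 of 15 patients (2 with three locations), and response in everyone else.

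The figures are a range of possibilities, not a forecast. They rest on assumed splits and response rates, and on 15 independent patients as the units.

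A reader might also infer that the efficacy conclusion is at risk. It is not: Section 7 makes the antitumour result descriptive, and no objective or sample size depends on the location comparison. One secondary P value is affected. The change is still worth making, because it is small and the test as named can report a location effect resting on one patient.

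**What to change.** In Section 8, replace the chi-squared P value by an exact two-tailed one at 0.05:

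- **Tables larger than 2 x 2:** the Fisher-Freeman-Halton test, or the exact permutation P value of the chi-squared statistic.
- **2 x 2 tables:** an unconditional exact test (Boschloo or Barnard), or Fisher's exact test with the mid-P value beside it.
- **If nodules are the unit:** allow for several nodules per patient, for example by permuting whole patients where location is constant within a patient, or by using one nodule per patient.

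The same sentence should name the location groups, the response split, the unit, and whether the earlier 17 patients are pooled. It should also say which P value decides if two are reported. For one non-responder the mid-P is k/(2n), so at k=1 it is 1/30 = 0.033 while Fisher's P is 0.067.

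The cost is a few lines of text, with no patients, visits or staff. Fisher's test alone would be conservative for yes/no response and could lose about 25 points of power, which is why the unconditional or mid-P version is offered. For four classes the power loss is small (about 5 points at 3/12, none at 5/10 or 7/8 in the case computed). If the software named in Section 8 lacks these tests, another package must be named.
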